- 3. Is willing to comply with all follow-up evaluations at the specified times.
- 4. Is ≥ 18 years old.
- 5. Provides written informed consent prior to enrollment in the study.

Angiographic Inclusion Criteria

Subjects must meet all of the following angiographic inclusion criteria. The implanting physician bases all angiographic inclusion criteria on visual determination at the time of the procedure.

- 1. Target lesion(s) located within the native SFA/proximal popliteal: distal point at least 3 cm above the cortical margin of the femur and proximal point at least 1 cm below the origin of the *profunda femoralis* measured by straight posteroanterior (PA) view for distal lesions, ipsilateral oblique view for proximal lesions. Refer to *Figure 1* for a diagram of a PA view of the distal femur and identification of the cortical margin.
- 2. Evidence of \geq 50% stenosis or restenosis (from PTA or adjunct therapy, not including stents or stent grafts), or occlusion of target lesion(s).
- 3. Target lesion(s) total length is ≥ 4 cm and ≤ 18 cm.
- 4. Target vessel diameter is ≥ 4.5 mm and ≤ 7.5 mm.
- 5. There is evidence of at least one runoff vessel to the ankle/foot of the limb to be treated that does not also require treatment for significant (> 50% stenosis or occlusion) stenosis during the index procedure.

Figure 1: PA View of Distal Femur and Definition of Cortical Margin

The line defining the cortical margin is perpendicular to the femur and includes the highest point in the cortical arch. No part of the lesion should be closer than 3 cm from the line defining the cortical margin.

General Exclusion Criteria

The subject must not meet any of the following general exclusion criteria.

- 1. Has undergone previous implantation of stent(s) or stent graft(s) in the target vessel.
- 2. Has a contraindication or known allergy to antiplatelet therapy, anticoagulants, thrombolytic drugs, contrast media or any other drug used in study according to the protocol.
- 3. Has known hypersensitivity to nickel-titanium.
- 4. Has bleeding diathesis, coagulopathy, known hypercoagulable condition, or refuses blood transfusion.
- 5. Female currently breastfeeding, pregnant, or of childbearing potential not using adequate contraceptive measures.
- 6. Has life expectancy of less than 1 year.
- 7. Has planned use of thrombectomy, atherectomy, brachytherapy or laser devices during procedure.
- 8. Has previously been enrolled in the DURABILITY PAS study.

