- 9. Has received endovascular treatment of target lesion by percutaneous transluminal angioplasty or any other means of previous endovascular treatment (e.g. cutting balloon, scoring balloon, cryoplasty, thrombectomy, atherectomy, brachytherapy or laser devices) within six months of the index procedure.
- 10. Has any planned surgical intervention or endovascular procedure 14 days before or 30 days after the index procedure.
- 11. Is currently participating in an investigational drug or another device study that has not completed the primary endpoint or that clinically interferes with the current study endpoints.
- 12. Has any co-morbid condition that precludes endovascular treatment.

Angiographic Exclusion Criteria

The subject must not meet any of the following angiographic exclusion criteria. The implanting physician bases all angiographic exclusion criteria on visual determination at the time of the procedure.

- 1. Exchangeable guidewire cannot cross the target lesion and/or re-enter true vessel lumen distal to lesion(s).
- 2. Presence of significant (> 50% stenosis or occlusion) ipsilateral common femoral stenosis.
- 3. Aneurysmal target vessel.
- 4. Presence of an acute intraluminal thrombus at the proposed lesion site.
- 5. Perforation, dissection or other injury of the access or target vessel requiring additional stenting or surgical intervention prior to start of PTA procedure.

6. Focal popliteal disease in the absence of femoral disease.

Patient Screening

It is expected that all potentially eligible patients be approached for enrollment in the study and be screened at the investigational site. Eligible patients will be given an explanation of the study, educated on the possible risks and benefits to participating, and be asked to provide written informed consent prior to any study-specific screening or testing. Patients will be informed that, despite signing the informed consent document, screening procedures may demonstrate that the patient is not a suitable candidate for the study.

Subject Enrollment

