The subject will undergo percutaneous revascularization of the SFA, which may include the proximal popliteal artery using the EverFlex device in conjunction with any FDA approved angioplasty balloon.

The following describes the required assessments and activities during the procedure.

Angiogram

A sheath will be inserted and after insertion the subject should be anticoagulated according to the discretion of the implanting physician. Selective angiography of the leg to be treated including the distal aorta, bilateral iliac, ipsilateral femoral, popliteal and tibial vessels (to the level of the ankle) will be performed to identify the anatomical characteristics of the vasculature and to best isolate and define the lesion. The distal-most point of the lesion should be at least 3 cm above the plane defining the cortical margin of the femur measured by straight posteroanterior (PA) view. (Refer to *Figure 1* for a diagram of a PA view of the distal femur, identifying the cortical margin.) Angiography must be conducted according the angiographic core lab protocol (see Manual of Operations).

During angiography the implanting physician will assess the subject for the angiographic inclusion and exclusion criteria. This includes verifying that the target lesion(s) total length is ≥ 4 cm and ≤ 18 cm. If the subject meets all the angiographic inclusion criteria and does not meet any of the angiographic exclusion criteria, the subject is enrolled when an exchangeable guidewire crosses the lesion and/or re-enters the true vessel lumen distal to the target lesion(s).

Angiograms will be obtained immediately prior to and after the angioplasty and stenting procedure to document pre- and post-treatment results. Copies of all angiograms must be sent to the angiographic core lab.

The angiographic core lab values will supersede the implanting physician's measurement assessments for data analysis purposes; however, the implanting physician's assessment will be used to determine subject eligibility at the time of enrollment.

Angioplasty and Stenting

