Standard PTA techniques will be followed for balloon dilatation prior to stent deployment and documented. Use of any devices other than PTA balloons, cutting balloons, and scoring balloons for recanalization (e.g. thrombectomy, atherectomy, brachytherapy or laser devices) during the index procedure will be considered a deviation of the clinical protocol. The use of PTA balloons, guidewires, and devices to facilitate placement of a guidewire distal to the target lesion, (e.g. Covidien VianceTM, Covidien EnteerTM, Cordis Frontrunner® CTO Re-Entry Catheter, and the Cordis Outback® LTDTM Re-Entry Catheter) during the index procedure will not be considered a deviation of the clinical protocol.

If the subject requires treatment of an atherosclerotic lesion in the iliac artery, this will be ALLOWED during the index procedure, either prior to or after the treatment of the SFA lesion. If the iliac artery treatment is completed prior to the SFA treatment, iliac artery treatment success (< 30% residual stenosis with no perforation, dissection or other injury requiring additional stenting or surgical intervention) must occur prior to the point of enrollment. If the iliac artery treatment is completed after the SFA treatment, < 30% iliac artery residual stenosis must be accomplished and verification of patency in the stented SFA segment must be completed via angiography. Documentation of the results for the iliac procedure either prior to or after the SFA treatment will be recorded.

The selection of the EverFlex stent size, deployment and withdrawal of the delivery system will follow the procedures described in the *Instructions for Use* provided in the Manual of Operations. Only one EverFlex stent should be used to treat the target lesion(s). The treatment of diffuse lesions is only allowed under the condition that the entire target area can be covered using a single stent. The distal-most point of the stent should be at least 3 cm above the line defining the cortical margin of the femur measured by straight posteroanterior (PA) view. The line defining the cortical margin is perpendicular to the femur and includes the highest point in the cortical arch.

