Descriptive statistics will be used to present the data and to summarize the results. Discrete variables will be presented using frequency distributions and cross-tabulations. Continuous variables will be summarized by presenting the number of observations (N), mean, standard deviation, median, minimum, and maximum values.

For adverse event reporting, the primary analysis will be based on subject counts, not event counts. A subject with more than one event will be counted only once toward the event rate based on the total number of subjects with adverse events.

Unless otherwise specified, statistical significance will be declared when p<0.05 for twosided tests and p<0.025 for one-sided tests such as the primary endpoint.

Analysis of Secondary Endpoints

For secondary endpoints, descriptive statistics will be provided. No formal statistical hypothesis testing will be performed. Categorical variables will be analyzed using frequency tabulation and event rate. For continuous variables, analysis will include mean, median, standard deviation, and ranges. Time-to-event variables including the primary endpoint and the secondary endpoint of freedom from stent fracture will be analyzed using survival analysis and reported at 1 year (365 days), 2 years (730 days) and 3 years (1095 days), with Kaplan-Meier plots provided.

Analysis of Ability to Pool Data Across Investigational Sites

This is a multi-center clinical study, with standardization of subject enrollment, data entry and adverse event reporting. All investigational sites will follow the requirements of a common protocol, data collection procedures and forms. To present the data from this clinical study in a summary form, a comparison across all sites will be completed to determine if the generated data could be pooled. The following variables will be completed to assess the appropriateness of pooling data from across all sites:

- Baseline demographics such as age and gender
- Lesion characteristics such as lesion length and percent stenosis

The distributions of the above variables across the sites will be tabulated. To detect site differences, t-tests or Wilcoxon's rank-sum test will be used for continuous variables and Fisher's exact test for categorical variables.

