b) development of pathologic Q waves on the ECG;

c) ECG changes indicative of ischemia (ST segment elevation or depression); or coronary artery intervention (e.g., coronary angioplasty).

d) Pathologic findings of an acute MI.

Criteria for established MI.

Any one of the following criteria satisfies the diagnosis for established MI:

- 1. Development of new pathologic Q waves on serial ECGs. The patient may or may not remember previous symptoms. Biochemical markers of myocardial necrosis may have normalized, depending on the length of time that has passed since the infarct developed.
- 2. Pathologic findings of a healed or healing MI.

² Alpert JS, Thygesen K, Antman E, Bassand JP. Myocardial infarction redefined--a consensus document of The Joint European Society of Cardiology/American College of Cardiology Committee for the redefinition of myocardial infarction. J Am Coll Cardiol. 2000 Sep;36(3):959-69.

Dissection	Description
Type A	Small radiolucent area within the lumen of the vessel disappearing
	with the passage of contrast material
Type B	Appearance of contrast medium parallel to the lumen of the vessel
	disappearing within a few cardiac cycles
Type C	Dissection protruding outside the lumen of the vessel persisting
	after passage of the contrast material
Type D	Spiral shaped filling defect with delayed runoff of the contrast
	material in the distal vessel
Type E	Persistent luminal filling defect with delayed runoff of the contrast
	material in the distal vessel
Type F	Filling defect accompanied by total coronary occlusion

National Heart, Lung and Blood Institute (NHLBI) Classification of Dissection³:

New York Heart Association (NYHA) Heart Failure Classification⁴:

Class	Description
Class I:	Subject has no physical limitation and is asymptomatic
Class II:	Subject has mild symptoms while doing light exercise or activities
	of daily living
Class III:	Subject has difficulty doing simple activities of daily living
Class IV:	Subject is frequently bed- or chair-ridden for most of the day and
	is too weak and short of breath to do simple activities

Occlusion: 100% stenosis within an artery.

Percent Stenosis: Native vessel diameter as measured at the most narrow point of the lesion divided by the estimated native vessel diameter (the mean of the vessel diameters proximal and distal to the lesion) at that location.

% Stenosis =

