Stent Migration: Substantial movement of the EverFlex stent from the initial deployment position, noted during the index procedure or via follow-up imaging. This does not include mis-measurement of the lesion, foreshortening or mis-sizing of the vessel.

Stent Misplacement: A stent that is not deployed at the target location.

Stroke: A neurological deficit lasting more than 24 hours, or lasting 24 hours or less with a brain imaging study showing infarction⁶.

Study Coordinator: Employee at investigational site who assists Principal Investigator with study activities as delegated by the Principal Investigator, including tracking subjects involved in the study, scheduling testing and follow-up visits, maintaining study records, completing and providing CRFs to the sponsor in a timely manner.

Sub-acute Closure: Vessel occlusion at the site of treatment between 24 hours and 4 weeks after successful index procedure.

Sub-Investigator(s): Physician(s) responsible for study activities in coordination with Principal Investigator and in accordance to the investigational plan. A site is not required to have a sub-investigator.

Target Lesion Revascularization: Any repeat invasive procedure, including angioplasty, stenting, endarterectomy, bypass, or thrombolysis, performed to open or increase the lumen diameter inside or within 10 mm of the previously treated lesion.

Clinically-Driven Target Lesion Revascularizations are those in which the patient has $a \ge 50\%$ diameter stenosis in the presence of recurrent symptoms or $a \ge 70\%$ stenosis without any symptoms (i.e. decreased ABI, symptomatic claudication, etc) in the treated segment.

Non-Clinically-Driven Target Lesion Revascularizations are those in which the patient undergoes a non-emergent revascularization for a diameter stenosis < 70% in the absence of recurrent claudication, a positive functional study (if available), or worsened ABI.

Target Vessel Revascularization: Any re-treatment by an invasive procedure, including angioplasty, stenting, endarterectomy, bypass, or thrombolysis, performed to open or increase the lumen diameter of the target vessel.

Clinically-Driven Target Vessel Revascularizations are those in which the patient has $a \ge 50\%$ diameter stenosis in the presence of recurrent symptoms or $a \ge 70\%$ stenosis without any symptoms (i.e. decreased ABI, symptomatic claudication, etc) in the treated vessel.

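### Protocol Section 10 defines percent stenosis as the lumen that remains, so an occlusion scores 0% where the adjacent entry says 100%

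*Protocol*

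**What the plan says.** Protocol Section 10.0, under Percent Stenosis, gives the definition twice. In words it is "Native vessel diameter as measured at the most narrow point of the lesion divided by the estimated native vessel diameter", where the denominator is the average of the diameters just above and just below the lesion. The displayed fraction has the same numerator and denominator, with no subtraction. The entry directly above it is "Occlusion: 100% stenosis within an artery", and the same section describes stenosis as a narrowing. Neither the protocol nor the SAP gives another formula.

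The thresholds that use a stenosis percentage are:

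- Angiographic inclusion (Section 4.0): target lesion stenosis of at least 50%, or occlusion.
- Angiographic exclusion (Section 4.0): "Presence of significant (> 50% stenosis or occlusion) ipsilateral common femoral stenosis".
- Iliac treatment success (Section 4.0, Angioplasty and Stenting): "< 30% residual stenosis with no perforation, dissection or other injury".
- Stent fracture categories A to C (synopsis, Sections 4.0 and 10.0, SAP Section 4): a cut at 50% restenosis, then occlusion.
- Clinically-driven TLR (Section 10.0): at least 50% diameter stenosis with recurrent symptoms, or at least 70% "stenosis without any symptoms (i.e. decreased ABI, symptomatic claudication, etc) in the treated segment". The target vessel revascularization entry uses the same cut-offs.

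In the analysis, the site-pooling comparison (Protocol Section 5.0, SAP Section 7.3) lists "Lesion characteristics such as lesion length and percent stenosis". On the source of the values, Section 4.0 states that "The angiographic core lab values will supersede the implanting" physician's measurements when data are analysed.

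**The concern.** A percentage that measures narrowing must rise as the lumen shrinks. The printed ratio falls. It therefore conflicts outright with the neighbouring Occlusion entry and is reversed relative to every threshold listed above.

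Two uses are at stake. The direct one is the by-site table of percent stenosis. Programmed as printed, that table would show enrolled lesions at 50% or less and occlusions at 0%, and would appear to contradict the inclusion rule. The possible one is endpoint adjudication. Section 4.0 has the CEC classify endpoint events by the protocol's definitions, and the Section 10.0 definition of clinically-driven TLR, a component of the primary composite, depends on a stenosis percentage.

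**Working it through.** **Inputs.** Let d be the diameter at the narrowest point and R the mean of the proximal and distal diameters (Section 10.0). The Occlusion entry sets 100% at d = 0. A reference of R = 6.0 mm is assumed for illustration; it lies inside the 4.5 to 7.5 mm range allowed by the inclusion criteria. The choice does not matter, because d/R has no scale: 4.5 and 7.5 mm give the same percentages.

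**Formulas.** Printed value P = 100 × d/R. True narrowing T = 100 × (1 − d/R). Hence P = 100 − T.

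**Reproducing the protocol's own figure.** For an occlusion, P = 100 × 0/6.0 = 0%. The Occlusion entry says 100%, so it is not reproduced. T = 100 × (1 − 0/6.0) = 100%, which matches.

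| d (mm), R = 6.0 | Printed P | True narrowing T |
|---|---|---|
| 0 (occlusion) | 0% | 100% |
| 1.2 | 20% | 80% |
| 1.8 | 30% | 70% |
| 3.0 | 50% | 50% |
| 4.2 | 70% | 30% |
| 6.0 (normal) | 100% | 0% |

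The two scales agree only at 50%.

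**Tabulated variable.** The inclusion range T = 50 to 100% becomes P = 50 to 0%. The mean becomes 100 minus the true mean. The SD is unchanged. Two-sided p-values from the t-test or Wilcoxon test named in the protocol are also unchanged, since replacing x by 100 − x only reverses the sign or the rank order. The site tests would therefore not reveal the error.

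**Thresholds, if P were applied literally.**

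- Iliac success, P < 30: 100 − T < 30, so T > 70%.
- TLR with symptoms, P ≥ 50: T ≤ 50. The classification reverses everywhere except at exactly 50%: narrowing below 50% would be added and narrowing above 50% missed.
- TLR without symptoms, P ≥ 70: T ≤ 30. Narrowing of 30% or less would be added and 70% or more missed; between 30% and 70% the classification does not change.

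In both TLR rules, the missed range includes occlusion only if the formula is used in place of the Occlusion entry.

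**Could the PDF conversion have lost a leading one-minus term?** That might explain the displayed fraction. It would not explain the prose definition, which states the same ratio independently. The revision table in Appendix D lists no change to this entry.

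**The case against.** The strongest reply is that this is an obvious drafting slip in a glossary, with no demonstrated effect on any result.

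- The thresholds and the Occlusion entry make the intended direction plain. The angiographic eligibility criteria are judged visually, so the formula is not used there.
- Percent stenosis is named in the analysis only as an example within the pooling comparison, which supports no endpoint and whose tests would be unaffected.
- Values for analysis come from the core laboratory under a manual that is not supplied. Nothing shows that the laboratory calculates from Section 10.0.
- The TLR entry does not cite the formula. The formula is worded for a native vessel, whereas TLR concerns a stented segment. The endpoint wording in the synopsis, Section 4.0 and SAP Section 4 rests on the return of symptoms and gives no percentage, so the 70% branch may not apply. Events added at little or no narrowing would require a repeat procedure on a nearly open vessel, which is improbable.

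All of this stands as a limit on the consequences, and the TLR route is no more than a possibility. None of it makes the definition correct. It remains the only formula in either document for a variable that both documents name for tabulation, and whether the core laboratory departs from it cannot be checked from the documents.

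**Conclusion.** The concern holds. The definition is wrong as written, in prose and in formula, and cannot be reconciled with the adjacent Occlusion entry. The size of the error is exact: the printed value is 100 minus the true narrowing.

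The consequence is limited. If the ratio were programmed as printed, a baseline table would be reversed. The number of TLR events affected cannot be computed: literal use would both add and remove events, so even the net direction is unknown, and actual misclassification is unlikely. Eligibility, site-comparison p-values, sample size, power and the performance goal do not depend on this formula. The conclusion assumes only that the printed prose is what the sponsor issued. This should be fixed, but it does not threaten the primary analysis on the evidence available.

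**What to change.** In Protocol Section 10.0, restate the entry in words and as a formula:

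% stenosis = [1 − (diameter at narrowest point ÷ mean of proximal and distal reference diameters)] × 100.

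This gives 100% for an occlusion and puts the scale in the same direction as the thresholds, none of which needs to change.

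Obtain written confirmation that the core laboratory and the CEC used this form, and that the percent stenosis tabulated under Protocol Section 5.0 and SAP Section 7.3 uses it. Only if the printed ratio was actually applied, re-tabulate the variable and re-adjudicate the TLRs classified with it.

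The cost is a one-line correction and one confirmation. No new data are needed.

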Appendix C: Declaration of Helsinki

Accessed: February 9, 2009. http://www.wma.net/e/policy/b3.htm

WORLD MEDICAL ASSOCIATION DECLARATION OF HELSINKI Ethical Principles for Medical Research Involving Human Subjects

Adopted by the 18th WMA General Assembly, Helsinki, Finland, June 1964, and amended by the: 29th WMA General Assembly, Tokyo, Japan, October 1975 35th WMA General Assembly, Venice, Italy, October 1983 41st WMA General Assembly, Hong Kong, September 1989 48th WMA General Assembly, Somerset West, Republic of South Africa, October 1996 52nd WMA General Assembly, Edinburgh, Scotland, October 2000 53th WMA General Assembly, Washington 2002 (Note of Clarification on paragraph 29 added) 55th WMA General Assembly, Tokyo 2004 (Note of Clarification on Paragraph 30 added) 59th WMA General Assembly, Seoul, October 2008

A. INTRODUCTION

1. The World Medical Association (WMA) has developed the Declaration of Helsinki as a statement of ethical principles for medical research involving human subjects, including research on identifiable human material and data. The Declaration is intended to be read as a whole and each of its constituent paragraphs should not be applied without consideration of all other relevant paragraphs.

2. Although the Declaration is addressed primarily to physicians, the WMA encourages other participants in medical research involving human subjects to adopt these principles.

3. It is the duty of the physician to promote and safeguard the health of patients, including those who are involved in medical research. The physician's knowledge and conscience are dedicated to the fulfillment of this duty.

4. The Declaration of Geneva of the WMA binds the physician with the words, "The health of my patient will be my first consideration," and the International Code of Medical Ethics declares that, "A physician shall act in the patient's best interest when providing medical care."

5. Medical progress is based on research that ultimately must include studies involving human subjects. Populations that are underrepresented in medical research should be provided appropriate access to participation in research.

6. In medical research involving human subjects, the well-being of the individual research subject must take precedence over all other interests.

7. The primary purpose of medical research involving human subjects is to understand the causes, development and effects of diseases and improve preventive, diagnostic and therapeutic interventions (methods, procedures and treatments). Even the best current

interventions must be evaluated continually through research for their safety, effectiveness, efficiency, accessibility and quality.

8. In medical practice and in medical research, most interventions involve risks and burdens.

9. Medical research is subject to ethical standards that promote respect for all human subjects and protect their health and rights. Some research populations are particularly vulnerable and need special protection. These include those who cannot give or refuse consent for themselves and those who may be vulnerable to coercion or undue influence.

10. Physicians should consider the ethical, legal and regulatory norms and standards for research involving human subjects in their own countries as well as applicable international norms and standards. No national or international ethical, legal or regulatory requirement should reduce or eliminate any of the protections for research subjects set forth in this Declaration.

B. PRINCIPLES FOR ALL MEDICAL RESEARCH

11. It is the duty of physicians who participate in medical research to protect the life, health, dignity, integrity, right to self-determination, privacy, and confidentiality of personal information of research subjects.

12. Medical research involving human subjects must conform to generally accepted scientific principles, be based on a thorough knowledge of the scientific literature, other relevant sources of information, and adequate laboratory and, as appropriate, animal experimentation. The welfare of animals used for research must be respected.

13. Appropriate caution must be exercised in the conduct of medical research that may harm the environment.

14. The design and performance of each research study involving human subjects must be clearly described in a research protocol. The protocol should contain a statement of the ethical considerations involved and should indicate how the principles in this Declaration have been addressed. The protocol should include information regarding funding, sponsors, institutional affiliations, other potential conflicts of interest, incentives for subjects and provisions for treating and/or compensating subjects who are harmed as a consequence of participation in the research study. The protocol should describe arrangements for post-study access by study subjects to interventions identified as beneficial in the study or access to other appropriate care or benefits.

15. The research protocol must be submitted for consideration, comment, guidance and approval to a research ethics committee before the study begins. This committee must be independent of the researcher, the sponsor and any other undue influence. It must take into consideration the laws and regulations of the country or countries in which the research is to be performed as well as applicable international norms and standards but these must not be allowed to reduce or eliminate any of the protections for research subjects set forth in this

Declaration. The committee must have the right to monitor ongoing studies. The researcher must provide monitoring information to the committee, especially information about any serious adverse events. No change to the protocol may be made without consideration and approval by the committee.

16. Medical research involving human subjects must be conducted only by individuals with the appropriate scientific training and qualifications. Research on patients or healthy volunteers requires the supervision of a competent and appropriately qualified physician or other health care professional. The responsibility for the protection of research subjects must always rest with the physician or other health care professional and never the research subjects, even though they have given consent.

17. Medical research involving a disadvantaged or vulnerable population or community is only justified if the research is responsive to the health needs and priorities of this population or community and if there is a reasonable likelihood that this population or community stands to benefit from the results of the research.

18. Every medical research study involving human subjects must be preceded by careful assessment of predictable risks and burdens to the individuals and communities involved in the research in comparison with foreseeable benefits to them and to other individuals or communities affected by the condition under investigation.

19. Every clinical trial must be registered in a publicly accessible database before recruitment of the first subject.

20. Physicians may not participate in a research study involving human subjects unless they are confident that the risks involved have been adequately assessed and can be satisfactorily managed. Physicians must immediately stop a study when the risks are found to outweigh the potential benefits or when there is conclusive proof of positive and beneficial results.

21. Medical research involving human subjects may only be conducted if the importance of the objective outweighs the inherent risks and burdens to the research subjects.

22. Participation by competent individuals as subjects in medical research must be voluntary. Although it may be appropriate to consult family members or community leaders, no competent individual may be enrolled in a research study unless he or she freely agrees.

23. Every precaution must be taken to protect the privacy of research subjects and the confidentiality of their personal information and to minimize the impact of the study on their physical, mental and social integrity.

24. In medical research involving competent human subjects, each potential subject must be adequately informed of the aims, methods, sources of funding, any possible conflicts of interest, institutional affiliations of the researcher, the anticipated benefits and potential risks of the study and the discomfort it may entail, and any other relevant aspects of the study. The potential subject must be informed of the right to refuse to participate in the study or to withdraw consent to participate at any time without reprisal. Special attention should be

given to the specific information needs of individual potential subjects as well as to the methods used to deliver the information. After ensuring that the potential subject has understood the information, the physician or another appropriately qualified individual must then seek the potential subject's freely-given informed consent, preferably in writing. If the consent cannot be expressed in writing, the non-written consent must be formally documented and witnessed.

25. For medical research using identifiable human material or data, physicians must normally seek consent for the collection, analysis, storage and/or reuse. There may be situations where consent would be impossible or impractical to obtain for such research or would pose a threat to the validity of the research. In such situations the research may be done only after consideration and approval of a research ethics committee.

26. When seeking informed consent for participation in a research study the physician should be particularly cautious if the potential subject is in a dependent relationship with the physician or may consent under duress. In such situations the informed consent should be sought by an appropriately qualified individual who is completely independent of this relationship.

27. For a potential research subject who is incompetent, the physician must seek informed consent from the legally authorized representative. These individuals must not be included in a research study that has no likelihood of benefit for them unless it is intended to promote the health of the population represented by the potential subject, the research cannot instead be performed with competent persons, and the research entails only minimal risk and minimal burden.

28. When a potential research subject who is deemed incompetent is able to give assent to decisions about participation in research, the physician must seek that assent in addition to the consent of the legally authorized representative. The potential subject's dissent should be respected.

29. Research involving subjects who are physically or mentally incapable of giving consent, for example, unconscious patients, may be done only if the physical or mental condition that prevents giving informed consent is a necessary characteristic of the research population. In such circumstances the physician should seek informed consent from the legally authorized representative. If no such representative is available and if the research cannot be delayed, the study may proceed without informed consent provided that the specific reasons for involving subjects with a condition that renders them unable to give informed consent have been stated in the research protocol and the study has been approved by a research ethics committee. Consent to remain in the research should be obtained as soon as possible from the subject or a legally authorized representative.

30. Authors, editors and publishers all have ethical obligations with regard to the publication of the results of research. Authors have a duty to make publicly available the results of their research on human subjects and are accountable for the completeness and accuracy of their reports. They should adhere to accepted guidelines for ethical reporting. Negative and inconclusive as well as positive results should be published or otherwise made publicly

available. Sources of funding, institutional affiliations and conflicts of interest should be declared in the publication. Reports of research not in accordance with the principles of this Declaration should not be accepted for publication.

C. ADDITIONAL PRINCIPLES FOR MEDICAL RESEARCH COMBINED WITH MEDICAL CARE

31. The physician may combine medical research with medical care only to the extent that the research is justified by its potential preventive, diagnostic or therapeutic value and if the physician has good reason to believe that participation in the research study will not adversely affect the health of the patients who serve as research subjects.

32. The benefits, risks, burdens and effectiveness of a new intervention must be tested against those of the best current proven intervention, except in the following circumstances:

- The use of placebo, or no treatment, is acceptable in studies where no current proven intervention exists; or
- Where for compelling and scientifically sound methodological reasons the use of placebo is necessary to determine the efficacy or safety of an intervention and the patients who receive placebo or no treatment will not be subject to any risk of serious or irreversible harm. Extreme care must be taken to avoid abuse of this option.

33. At the conclusion of the study, patients entered into the study are entitled to be informed about the outcome of the study and to share any benefits that result from it, for example, access to interventions identified as beneficial in the study or to other appropriate care or benefits.

34. The physician must fully inform the patient which aspects of the care are related to the research. The refusal of a patient to participate in a study or the patient's decision to withdraw from the study must never interfere with the patient-physician relationship.

35. In the treatment of a patient, where proven interventions do not exist or have been ineffective, the physician, after seeking expert advice, with informed consent from the patient or a legally authorized representative, may use an unproven intervention if in the physician's judgment it offers hope of saving life, re-establishing health or alleviating suffering. Where possible, this intervention should be made the object of research, designed to evaluate its safety and efficacy. In all cases, new information should be recorded and, where appropriate, made publicly available.

Revision Level	Change Order	Description of Changes
1.0		Initial Release
2.0		Changes made to reduce number of subjects, revise inclusion/exclusion criteria, and change study sponsor to Covidien from ev3.
3.0		Updated number of subjects to 108 enrolled subjects in the protocol synopsis, Section 1.0 Introduction, and Section 5.0 Statistical Method . Appendix A has also been updated to reflect new Medtronic Contact Information.
3.1		 Protocol revision: Protocol version updated to version 3.1 Protocol version date updated to 17November2016 Updated Table 9, Approximation to Possible Outcomes and Corresponding 97.5% Lower Confidence Bound. Formatting to remove blank tables. Added table header (table 10) to Sample Size Freedom from Stent Fracture table, and updated all table numbers.

